4.5. Subject and Study Completion

A completed subject is defined as one who has completed all phases of the study (see Section 3.1 and [Table 5](#)). Subjects who receive but who discontinue from IP will not be considered withdrawn from the study and should remain in the study and continue to be followed for efficacy and safety (see Section 4.4.2).

The end of the study is defined as the neonatal record review at 28 days post EDD for the last subject randomly assigned to and treated with IP.

5. STUDY TREATMENTS

5.1. Investigational Product and Other Study Treatment

Retosiban for IV administration will be supplied as solution for infusion, consisting of a clear colorless solution of retosiban at a concentration of 15 mg/mL in 56% vol/vol ethanol/acetate buffer concentrate. The solution is sterilized by filtration and aseptically filled into glass vials. The vials are sealed with rubber stoppers and aluminum seals with a plastic flip-off lid. The solution for infusion should be stored refrigerated at 2°C to 8°C (36°F to 46°F), protected from light. Each single-use 5-mL vial contains 75 mg retosiban as solution for infusion (see [Table 3](#)). The contents of the label will be in accordance with all applicable regulatory requirements.

Under normal conditions of handling and administration, retosiban IP is not expected to pose significant safety risks to site staff. Take adequate precautions to avoid direct eye or skin contact and the generation of aerosols or mists. Notify the monitor of any unintentional occupational exposure. A Material Safety Data Sheet describing the occupational hazards and recommended handling precautions will be provided to site staff if required by local laws or will otherwise be available from GSK upon request.

At the clinical study site, the volume required to make up the dose is withdrawn from 1 or more drug product vials and aseptically transferred into a 0.9% sodium chloride (NaCl) infusion bag to get the required concentration. The final mixture is a clear, colorless to slightly colored solution. The infusion solution is chemically stable for up to 48 hours under ambient conditions. Chemical stability up to 48 hours has also been established for the reconstituted and diluted solution in contact with representative IV administration sets under ambient conditions.

Atosiban (Tractocile, Ferring Pharmaceuticals) active comparator will be provided to the site. Atosiban is a marketed product that is a clear, colorless solution for infusion that contains atosiban at 6.75 mg/0.9 mL. Each single-use, 5-mL vial contains 37.5 mg of atosiban. The solution for infusion should be stored at 2°C to 8°C (36°F to 46°F), protected from light. Information on atosiban, including list of excipients, can be found in the product package inserts found in the summary of characteristics [[Tractocile SmPC](#),

2013]. At the clinical study site, the volume required to make up the dose is withdrawn from 1 or several drug product vials and aseptically transferred into a 0.9% NaCl infusion bag to get the required concentration. The final mixture is a clear, colorless to slightly colored solution. The infusion solution is chemically stable for up to 24 hours under ambient conditions.

Because the IV dosing instructions for retosiban and atosiban differ, a double-dummy technique will be used to ensure blinding. For subjects randomized to retosiban, an unblinded pharmacist or other qualified individual will prepare the retosiban IV solution and a placebo infusion matched for the atosiban loading (bolus) dose and continuous infusion. Likewise, subjects randomized to atosiban will receive the atosiban loading (bolus) dose and continuous infusion and a placebo infusion matched for retosiban IV administration (see [Table 3](#); detailed instructions are provided in the Study Pharmacy Manual).

Atosiban solution for injection will be supplied by the unblinded pharmacist or other qualified individual as a prefilled syringe, whereas a prefilled syringe with 0.9% NaCl solution will be used for the matched placebo. Normal saline (0.9% NaCl) solution will be used for preparing the retosiban or atosiban admixtures for continuous infusion (see [Table 4](#)). Normal saline (0.9% NaCl) solution will also be used as the placebo solution matched to the infusion rates for retosiban or atosiban (see [Table 4](#); detailed instructions are provided in the Study Pharmacy Manual). The normal saline solutions will be provided by the investigative center.

Details of the dose preparation are described in the Pharmacy Reference Manual. The infusion bags and syringes containing the solution for administration will be clearly labeled by site staff with the protocol number, subject number, infusion rate, and dosing session number.

Investigational product must be stored in a secure area under the appropriate physical conditions for the product. Access to and administration of the IP will be limited to the investigator and authorized site staff. Investigational product must be dispensed or administered only to subjects enrolled in the study and in accordance with the protocol.

[Table 3](#) and [Table 4](#) summarize the retosiban and atosiban IP, respectively, and other study treatment.

Table 3 Retosiban Investigational Product and Other Study Treatment

Product Name	Retosiban Solution for Infusion	PTM IV Solution (0.9% NaCl)
Drug product description	Clear, colorless solution for infusion in a 5-mL vial containing 75 mg of retosiban	A placebo-matched glass vial is not provided.
Unit dose strengths / Dosage levels	Retosiban 15 mg/mL The total dose given over 48 hours should not exceed 300 mg at the 6-mg/hour infusion rate and 582 mg at the 12-mg/hour infusion rate.	0.9% NaCl matched for the retosiban loading dose and continuous infusion rates
Route of administration	IV	IV
Preparation instructions	Withdraw 10-mL solution from a 500-mL 0.9% NaCl infusion bag and discard the solution. Replace discarded solution with 10 mL retosiban 15-mg/mL concentrate solution for infusion from two 5-mL vials to obtain a concentration of 0.3 mg/mL (150 mg retosiban in 500 mL 0.9% NaCl). The reconstituted product is a clear, colorless solution without particles. Label the IV bag with protocol number, subject number, infusion rate, and dosing session number. Once the vial has been opened, the dilution must be performed immediately. Diluted solution for IV administration should be used within 24 hours after preparation. If an infusion bag with a different volume is used, a proportional calculation should be made for the preparation. See the Study Pharmacy Manual for detailed instructions.	The placebo admixture will consist of a 0.9% NaCl infusion bag, labeled with the protocol number, subject number, infusion rate, and dosing session number. The volume of the 0.9% NaCl infusion bag should be matched to the 0.9% NaCl infusion bag volume used for the retosiban admixture. See Study Pharmacy Manual for detailed instructions.
Dosing instructions	The retosiban 6-mg loading dose is administered at an infusion rate of 240 mL/hour for 5 minutes. After 5 minutes, the infusion rate is reduced to 20 mL/hour to deliver retosiban at a rate of 6 mg/hour for the remainder of the 48-hour treatment period. An adequate treatment response is based on (1) a clinically relevant reduction of contraction frequency and/or intensity or (2) no change in the cervical examination. An inadequate response is defined as a clinically significant change in the cervical examination or no significant reduction in contraction frequency and/or intensity. For subjects with an inadequate response any time after the first hour of treatment, investigators should administer another 6-mg loading dose by increasing the infusion rate to 240 mL/hour for 5 minutes, after which the	Intravenous administration of the 0.9% NaCl solution will be matched to the loading dose rate of 240 mL/hour for 5 minutes, after which the infusion rate is set to 20 mL/hour. An adequate treatment response is based on (1) a clinically relevant reduction of contraction frequency and/or intensity or (2) no change in the cervical examination. An inadequate response is defined as a clinically significant change in the cervical examination or no significant reduction in contraction frequency and/or intensity. For subjects with an inadequate response any time after the first hour of treatment, investigators should administer another loading dose by increasing the infusion rate to 240 mL/hour for 5 minutes, after which the infusion rate is set to 40 mL/hour. Investigators will be required to indicate

Product Name	Retosiban Solution for Infusion	PTM IV Solution (0.9% NaCl)
	
infusion rate is set to 40 mL/hour in order to deliver retosiban at a rate of 12 mg/hour. Investigators will be required to indicate in the eCRF the reason or reasons for a dose increase. A subject's response should be assessed for at least 1 hour following a dose increase before a decision is made to discontinue randomized treatment due to an inadequate response.
 
For subjects receiving concomitant treatment with a potent CYP3A4 inhibitor, the retosiban 3-mg loading dose is administered at an infusion rate of 120 mL/hour for 5 minutes. After 5 minutes, the infusion rate is reduced to 6.7 mL/hour to deliver retosiban at a rate of 2 mg/hour. For subjects with an inadequate response any time after the first hour, an additional 1-mg loading dose is administered by increasing the infusion rate to 40 mL/hour over 5 minutes after which the infusion rate is set to 10 mL/hour to deliver retosiban at 3 mg/hour for the remainder of the 48-hour treatment period.
 
For subjects receiving concomitant treatment with a CYP3A4 inducer, the retosiban 8.5-mg loading dose is administered at an infusion rate of 340 mL/hour for 5 minutes. After 5 minutes, the infusion rate is reduced to 28 mL/hour to deliver retosiban at a rate of 8.5 mg/hour. For subjects with an inadequate response any time after the first hour, an additional 3.5-mg loading dose is administered by increasing the infusion rate to 140 mL/hour for 5 minutes. After 5 minutes, the infusion rate is reduced to 40 mL/hour to deliver retosiban at a rate of 12 mg/hour.
 
A list of strong, moderate, and weak CYP3A4 inhibitors and inducers is provided in Appendix 3. See the Study Pharmacy Manual for detailed instructions.
	
in the eCRF the reason or reasons for a dose increase. A subject's response should be assessed for at least 1 hour following a dose increase before a decision is made to discontinue randomized treatment due to an inadequate response.
 
For subjects receiving concomitant treatment with a potent CYP3A4 inhibitor, the loading dose is administered at an infusion rate of 120 mL/hour for 5 minutes. After 5 minutes, the infusion rate is reduced to 6.7 mL/hour. For patients with an inadequate response any time after the first hour, an additional loading dose is administered by increasing the infusion rate to 40 mL/hour over 5 minutes, after which the infusion rate is set to 10 mL/hour.
 
For subjects receiving concomitant treatment with a CYP3A4 inducer, the loading dose is administered over 5 minutes at an infusion rate of 340 mL/hour for 5 minutes. After 5 minutes, the infusion rate is reduced to 28 mL/hour. For patients with an inadequate response any time after the first hour, an additional loading dose is administered by increasing the infusion rate to 140 mL/hour for 5 minutes. After 5 minutes, the infusion rate is reduced to 40 mL/hour.
 
A list of strong, moderate, and weak CYP3A4 inhibitors and inducers is provided in Appendix 3. See Study Pharmacy Manual for detailed instructions.

Manufacturer / Source of procurement	GSK	Not applicable – to be sourced locally

CYP3A4 = cytochrome P450 3A4 enzyme; eCRF = electronic case report form; IV = intravenous; GSK = GlaxoSmithKline; NaCl = sodium chloride; PTM = placebo to match.

Table 4 Atosiban Investigational Product and Other Study Treatment

Product Name	Atosiban Solution for Injection and Atosiban Solution for Infusion	PTM IV Solution (0.9% NaCl)
Drug product description	Clear, colorless solution for injection in a 0.9-mL vial containing 6.75 mg of atosiban Clear, colorless concentrate for solution for infusion in a 5-mL vial containing 37.5 mg atosiban	A placebo-matched 0.9-mL vial is not provided. A placebo-matched 5-mL vial is not provided.
Unit dose strengths / Dosage levels	Atosiban 6.75 mg/0.9 mL (solution for injection) Atosiban 7.5 mg/mL (concentrate solution for infusion) The total dose given over 48 hours should not exceed 330 mg.	0.9% NaCl for injection matched for the atosiban loading dose and continuous infusion rates
Route of administration	IV	IV
Preparation instructions	Withdraw 0.9 mL of a 0.9-mL labeled vial of atosiban 6.75 mg/0.9 mL solution for injection into a syringe. Label the syringe with the protocol number, subject number, infusion rate, and dosing session number. Withdraw 25-mL solution from a 250-mL 0.9% NaCl infusion bag and discard the solution. Replace the solution with 25 mL of atosiban 7.5-mg/mL concentrate solution for infusion from five 5-mL vials to obtain a concentration of 0.75 mg/mL (187.5 mg atosiban in 250 mL 0.9% NaCl). The reconstituted product is a clear, colorless solution without particles. Label the IV bag with protocol number, subject number, infusion rate, and dosing session number. Prepare new 250-mL bags in the same manner as described to allow the infusion to be continued. If an infusion bag with a different volume is used, a proportional calculation should be made for the preparation. Once the vial has been opened, the dilution must be performed immediately. Diluted solution for IV administration should be used within 24 hours after preparation. See the Study Pharmacy Manual for detailed instructions.	Withdraw 0.9 mL of 0.9% NaCl solution for injection into a syringe. Label the syringe with the protocol number, subject number, infusion rate, and dosing session number. The placebo admixture for continuous infusion will consist of a 0.9% NaCl infusion bag, labeled with the protocol number, subject number, infusion rate, and dosing session number. The volume of the 0.9% NaCl infusion bag should be matched to the 0.9% NaCl infusion bag volume used for the atosiban admixture. See Study Pharmacy Manual for detailed instructions

Product Name	Atosiban Solution for Injection and Atosiban Solution for Infusion	PTM IV Solution (0.9% NaCl)
Dosing instructions	
Atosiban is administered in 3 successive stages.
 
Administer an initial bolus dose of 6.75 mg slowly over 1 minute using the 6.75-mg/0.9 mL solution for injection syringe.
 
After the bolus dose, administer atosiban at a continuous infusion rate of 24 mL/hour (18 mg/hour) for 3 hours.
 
After 3 hours, the infusion rate is reduced to 8 mL/hour (6 mg/hour) for the remainder of the 48-hour treatment period.
 
See the Study Pharmacy Manual for detailed instructions.
	
The matched placebo is administered in 3 successive stages.
 
Using a prefilled syringe, administer 0.9 mL of 0.9% NaCl slowly over 1 minute.
 
After the bolus dose, administer 0.9% NaCl at a continuous infusion rate of 24 mL/hour for 3 hours.
 
After 3 hours, the infusion rate is reduced to 8 mL/hour for the remainder of the 48-hour treatment period.
 
See Study Pharmacy Manual for detailed instructions.

Manufacturer / Source of procurement	To be sourced locally	Not applicable – to be sourced locally

IV = intravenous; NaCl = sodium chloride; PTM = placebo to match.

5.1.1. Concurrent Administration of Investigational Product With Strong CYP3A4 Inhibitors or Strong CYP3A4 Inducers

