5.1.1.1. Retosiban

Retosiban undergoes oxidative metabolism, primarily mediated by CYP3A4 (see Section 3.2.1.1). As a result, concomitant administration of drugs that are strong CYP3A4 inhibitors may result in increased exposure to retosiban. When given orally, retosiban exposure was increased 8.7-fold, as measured by AUC, in the presence of ketoconazole, a strong CYP3A4 inhibitor.

To achieve exposures comparable to those achieved with the retosiban 6-mg/hour dosing regimen, retosiban should be administered as a 3-mg loading dose over 5 minutes followed by a 2-mg/hour continuous infusion in subjects who are being treated concomitantly with a strong CYP3A4 inhibitor (see Section 5.8.1.5). Using a 500-mL retosiban admixture with a 0.3-mg/mL concentration, the retosiban 3-mg loading dose will be administered at an infusion rate of 120 mL/hour for 5 minutes. After 5 minutes, the infusion rate will be reduced to 6.7 mL/hour to deliver retosiban at a rate of 2 mg/hour. If a dose increase is needed due to lack of response, an additional loading dose of 1 mg over 5 minutes followed by an increase to 3 mg/hour for the remainder of the 48-hour treatment period is an acceptable dosing regimen to use in the presence of a strong CYP3A4 inhibitor.

For subjects chronically taking a drug known to be a CYP3A4 inducer, the initial dose of retosiban should be an 8.5-mg loading dose over 5 minutes followed by an 8.5-mg/hour continuous infusion for the remainder of the 48-hour treatment period. If a dose increase is needed due to lack of response, an additional 3.5-mg loading dose over 5 minutes should be administered followed by an increase to 12 mg/hour for the remainder of the 48-hour treatment period.

A list of strong, moderate, and weak CYP3A4 inhibitors and inducers is provided in Appendix 3.

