5.8.1.6. Strong CYP3A4 Inducers

Drugs that are strong CYP3A4 inducers and cannot be temporarily discontinued are permitted. Administration of strong CYP3A4 inducers concomitantly with IP requires an adjustment to the retosiban dosing regimen (see Section 5.1.1). A list of strong, moderate, and weak CYP3A4 inducers is provided in [Appendix 3](#).

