11.3. Appendix 3: Cytochrome P450 3A4 Enzyme Inhibitors and Inducers

Medications that are considered cytochrome P450 3A4 enzyme (CYP3A4) inducers and inhibitors are permitted; however, concomitant administration of strong CYP3A4 inducers or strong inhibitors with the investigational product requires an adjustment to the retosiban dosing regimen (see Protocol Section 5.1 and Section 5.1.1.1).

[figure not shown]
Following is a list of CYP3A4 inhibitors and inducers, each classified as strong, moderate, or weak on the basis of changes in the AUC_i/AUC (area of the curve of substrate in the presence of an inhibitor/area under the curve of substrate in a control condition). This is not an exhaustive list; the summary of product characteristics and/or the package insert for each concomitant medication should be reviewed to determine if the product is a strong CYP3A4 inducer or inhibitor.

Strong ¹ (Requires Adjustment to Dosing Regimen)	Moderate ²	Weak ³
Inhibitors		
Amprenavir	Aprepitant	Amlodipine
Atazanavir	Cimetidine	Atomoxetine
Clarithromycin	Darunavir	Atorvastatin
Conivaptan	Diltiazem	Azithromycin
Fosamprenavir	Erythromycin	Bicalutamide
Grapefruit juice ⁴	Fluconazole	Chlorzoxazone
Indinavir	Imatinib	Cilostazol
Itraconazole	Nifedipine	Cyclosporine
Ketoconazole	Tofisopam	Darifenacin
Nefazodone	Verapamil	Dasatinib
Nelfinavir		Ezetimibe
Ritonavir		Fentanyl
Saquinavir		Fluvoxamine
Telithromycin		Gemfibrozil
Troleandomycin		Isoniazid
Voriconazole		Lacidipine
		Omeprazole
		Posaconazole
		Propiverine

Strong¹ (Requires Adjustment to Dosing Regimen)	Moderate²	Weak³
		Propofol
		Quinidine
		Ranitidine
		Ranolazine
		Roxithromycin
		Tabimorelin
Inducers		
Strong¹ (Requires Adjustment to Dosing Regimen)	Moderate²	Weak³
Carbamazepine	Bosentan	Aprepitant
Efavirenz	Etravirine	Amprenavir
Phenytoin	Nafcillin	Avasimibe
Rifampin	Nevirapine	Dexamethasone
St. Johns Wort	Phenobarbital	Glycyrrhizin
		Modafinil
		Oxcarbazepine
		Pioglitazone
		Prednisone
		Rifabutin
		Rufinamide

1. Strong inhibitor: >5 AUCi/AUC (area of the curve of substrate in the presence of an inhibitor/area under the curve of substrate in a control condition); strong inducer: <0.2 AUCi/AUC. Co-administration of the investigational product with a strong inhibitor or strong inducer requires an adjustment to the retosiban dosing regimen.
2. Moderate inhibitor: 2 to 5 AUCi/AUC; moderate inducer: 0.2 to 0.5 AUCi/AUC.
3. Weak inhibitor: <2 AUCi/AUC; weak inducer: 0.5 to 0.8 AUCi/AUC.

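### Table 3 triggers the 8.5-mg retosiban regimen for any CYP3A4 inducer, while the rest of the protocol limits the adjustment to strong inducers (minor)

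*Protocol*

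**What the plan says.** The retosiban column of Table 3 reads "For subjects receiving concomitant treatment with a CYP3A4 inducer, the retosiban 8.5-mg loading dose is administered", at 340 mL/hour for 5 minutes and then 28 mL/hour. The placebo column mirrors it: "For subjects receiving concomitant treatment with a CYP3A4 inducer, the loading dose is administered over 5 minutes at an infusion rate of 340 mL/hour". In the same cells, the inhibitor rule is limited to *potent* inhibitors. Both columns then add that "A list of strong, moderate, and weak CYP3A4 inhibitors and inducers is provided in Appendix 3", without saying which tier triggers a change.

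Section 5.1.1.1 opens its inducer rule with "For subjects chronically taking a drug known to be a CYP3A4 inducer". The sentence has no strength word, but the section falls under the heading "Concurrent Administration of Investigational Product With Strong CYP3A4 Inhibitors or Strong CYP3A4 Inducers".

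Elsewhere the rule is explicit. Section 5.8.1.6: "Administration of strong CYP3A4 inducers concomitantly with IP requires an adjustment to the retosiban dosing regimen". The mitigation column of Table 1 says the same. In Appendix 3 the *Strong* column is marked as the one that requires adjustment, and footnote 1 states: "Co-administration of the investigational product with a strong inhibitor or strong inducer requires an adjustment to the retosiban dosing regimen". Appendix 3 lists dexamethasone as a weak inducer.

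Efavirenz is *moderate* in the data column of Table 1, *potent* in Section 3.2.1.1, and in the *Strong* inducer column of Appendix 3.

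**The concern.** Table 3 is an operative dosing instruction: it sets the pump rate for retosiban and for its matched placebo. A reader who follows it as written would apply the 8.5-mg regimen to users of weak and moderate inducers as well as strong ones.

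The case with practical reach is antenatal dexamethasone. Sections 3.2.1.2 and 4.4.2 name betamethasone and dexamethasone as the antenatal steroids. Section 3.2.1.3 says that guidelines recommend a course for women at 24 to 34 weeks who are at risk of delivery within 7 days, which is close to a description of the trial population. The drug dose would change only in the retosiban arm; in the atosiban arm the same instruction changes a saline rate.

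Two readers of the same protocol could therefore start the same woman at different rates, and there would be no single rule for calling either rate a deviation.

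**Working it through.** **Where the strength word appears**

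| Place | Inducer trigger | Use |
|---|---|---|
| Table 3, retosiban and placebo columns | no strength word | concomitant |
| 5.1.1.1, sentence | no strength word | chronic |
| 5.1.1, heading over 5.1.1.1 | strong | concurrent |
| 5.8.1.6 | strong | concomitant |
| Table 1, mitigation column | strong | concomitant |
| Appendix 3, text, column header, footnote 1 | strong | concomitant |

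The omission is specific to inducers. The inhibitor rule carries *potent* in Table 3 and *strong* in 5.1.1.1. Appendix 3 sends the reader to Sections 5.1 and 5.1.1.1 for the strong-only adjustment, and the operative sentences there are the ones that leave the word out.

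**Reproducing the plan's pump settings** (admixture 0.3 mg/mL, Table 3)

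- Standard load: 240 mL/h × 5/60 h × 0.3 = 6.0 mg. Infusion: 20 × 0.3 = 6.0 mg/h.
- Inducer load: 340 × 5/60 × 0.3 = 8.5 mg, as stated.
- Inducer infusion: 28 × 0.3 = 8.4 mg/h, against the stated 8.5. The exact rate would be 8.5/0.3 = 28.3 mL/h, so this is rounding.

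**Size of the literal reading**

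- Rate ratio: 8.5/6 = 1.42 as stated; 8.4/6 = 1.40 as pumped.
- Infusion time after the load: 48 h − 5 min = 47.917 h.
- Standard total, no step-up: 6 + 6 × 47.917 = 293.5 mg.
- Inducer total, no step-up: 8.5 + 8.4 × 47.917 = 411.0 mg, or 8.5 + 8.5 × 47.917 = 415.8 mg at the stated rate.
- Difference: 117.5 to 122.3 mg over 48 hours.

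**Efavirenz**

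Table 1 reports a 42% rise in retosiban clearance with efavirenz. Scaling the standard rate gives 6 × 1.42 = 8.52 mg/h, so the 8.5-mg regimen matches the one inducer for which the protocol gives retosiban data. The protocol uses *potent* and *strong* interchangeably: ketoconazole is strong in Table 1 and 5.1.1.1, and potent in 3.2.1.1. The conflict is therefore between two classes, moderate in Table 1 and strong or potent elsewhere.

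**The case against.** The best case against the point is that the intended rule is easy to recover. In the current protocol, dexamethasone is identified as an inducer only in Appendix 3. There it stands in the weak column, beside a strong column marked as the one needing adjustment, and Table 3 points to that list in the same cell. Section 5.1.1.1 sits under a heading limited to strong inducers, and its chronic-use wording on its face excludes a single steroid course. Table 3 also defers to the Study Pharmacy Manual, which is not available here and may be clearer.

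All of this stands, and it is why the grade is minor. It does not remove the fault: the table that gives the pump rates states a wider rule than every other place that sets its scope, and uses a different trigger from the section that should govern it.

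A reader might infer two stronger conclusions that the documents do not support:

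- That efavirenz users risk the wrong dose because of the label conflict. Table 3 as written, 5.1.1.1 and Appendix 3 all lead to the 8.5-mg regimen. With *strong* inserted, Appendix 3 still lists efavirenz as strong, so the dose is unchanged. The word *moderate* stands in a background data column.
- That the missing word breaches the retosiban dose cap. Any total reached on the inducer regimen is reached equally by a strong-inducer user treated correctly, so it does not follow from the omission.

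**Conclusion.** The inconsistency is real and is in the current text. Table 3 is wrong as written, in both columns; 5.1.1.1 needs the same word but is rescued by its heading. The severity is minor.

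The size, about 40% on the starting rate and roughly 118 to 122 mg over 48 hours without a step-up, applies only if someone follows Table 3 literally and disregards Appendix 3 and 5.1.1.1. The resulting rate stays within the permitted 6 to 12 mg/hour. These are differences in dose, not exposure: the documents give neither the number of women on dexamethasone nor its effect on retosiban. Nothing here shows that any woman was dosed this way, and sample size, alpha and power are untouched.

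The SAP (Sections 1 and 2.1) records that the trial was terminated, with 97 enrolled, so an edit cannot change past dosing. The rule still matters for reporting, because SAP Section 8.2.2 plans a listing of reasons for investigational product deviations, with details to be settled before database lock.

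**What to change.** 1. In both Table 3 columns and in Section 5.1.1.1, insert *strong* before CYP3A4 inducer.
2. Use one trigger in both places, that of 5.1.1.1: subjects chronically taking a strong CYP3A4 inducer. Table 1, Section 5.8.1.6 and Appendix 3 refer the reader to these sections and can stand.
3. State that a short antenatal dexamethasone course needs no adjustment of the retosiban regimen.
4. As a consistency edit with no dosing effect, change the efavirenz label in Table 1 from moderate to match Section 3.2.1.1 and Appendix 3, and keep efavirenz on the 8.5-mg regimen.

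The cost is a few words, plus a check that the Study Pharmacy Manual says the same. With the trial closed, the same rule should be written into the deviation criteria used for the SAP listing.
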